6.4.3 Clinical Laboratory Evaluations

Clinical laboratory evaluations (hematology, chemistry, coagulation, thyroid panel and urinalysis) will be summarized using descriptive statistics for select laboratory parameters including absolute measurements and changes from baseline by visit.

For laboratory parameters, shift tables (with categories of low, normal, high based on normal ranges) from baseline to post-baseline assessments may be produced. Both scheduled and unscheduled post-baseline visits will be considered in tabulations.

A listing will be generated for subjects potentially meeting Hy's Law criteria (Total Bilirubin \geq (2×ULN) and AST or ALT > (3×ULN) at any time during the study). Graphical displays may also be provided to help identify potential Hy's Law cases.

Clinical laboratory evaluations will be listed by subject.

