International Normalized Ratio (INR) and prothrombin time (PT) ≤1.5×ULN or activated partial thromboplastin time (aPTT) ≤1.5×ULN, unless undergoing anticoagulation therapy

d. Liver:

- AST and ALT $\leq 2 \times ULN$ or $\leq 2.5 \times ULN$ with liver metastasis
- Bilirubin ≤1.5×ULN, unless genetic cause of elevated bilirubin is known (such as Gilbert's Syndrome).

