9.2.4.3. Laboratory Values

Descriptive statistics for laboratory test values and changes from baseline at each visit will be tabulated and, in some cases, presented graphically. Additional analyses based on shift from baseline in test values in multiples of the lower/upper limit of normal range (LLN/ULN) of a parameter will be detailed in the statistical analysis plan.

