8 CHANGES FROM PROTOCOL-SPECIFIED ANALYSIS

There are no changes from the analysis specified in protocol v8.0.

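### SAP 6.4.3 offers only optional low/normal/high laboratory shift tables, although Protocol 9.2.4.3 commits the SAP to shifts in multiples of LLN/ULN and SAP 8 declares no change

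*SAP*

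**What the plan says.** Protocol 9.2.4.3 (Laboratory Values) plans descriptive statistics and changes from baseline. For further analyses it says that "shift from baseline in test values in multiples of the lower/upper limit of normal range (LLN/ULN) of a parameter will be detailed", and names the SAP as the place where this will be done.

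SAP 6.4.3 (Clinical Laboratory Evaluations) says instead that "shift tables (with categories of low, normal, high based on normal ranges) from baseline to post-baseline assessments may be produced". It counts scheduled and unscheduled post-baseline visits in the tabulations. No section of the SAP defines a shift by multiples of LLN or ULN. The one laboratory output there that uses ULN multiples is the Hy's Law listing, which requires total bilirubin of at least 2×ULN together with AST or ALT above 3×ULN.

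SAP 8 states: "There are no changes from the analysis specified in protocol v8.0".

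Protocol 5.1 (criterion 8) allows out-of-range liver tests at entry. AST and ALT may be up to 2×ULN, or 2.5×ULN "with liver metastasis". The bilirubin limit reads "Bilirubin ≤1.5×ULN, unless genetic cause of elevated bilirubin is known", so no upper limit is stated for a subject with such a cause.

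**The concern.** A definite protocol commitment has become a coarser and optional SAP table, and the section meant to record departures says there are none.

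The coarser scale matters most for liver tests. A three-category table registers only the crossing of a reference limit. A subject who starts above ULN has no higher category to move into, and a subject who starts normal gets the same entry whether the worst value is slightly or far above ULN. The protocol's own liver criteria (section 4.1.5) are written in multiples of ULN, so the planned shift table cannot be read against them.

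At stake is the readability of the laboratory safety summary. Tests are run at local laboratories (Protocol Appendix 2), so reference ranges may differ between sites, and scaling to the limit of normal makes values comparable. Escalation cohorts have 3 to 6 subjects (up to 15 with backfill), and in groups of that size by-visit means show a single large rise poorly.

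**Working it through.** The plan gives no figure to reproduce. The check classifies the same values in two ways.

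**Inputs**
- Baselines at the entry limits (Protocol 5.1): ALT 2.0×ULN, or 2.5×ULN with liver metastasis; bilirubin 1.5×ULN. A normal baseline of 1.0×ULN is added for contrast.
- Thresholds (Protocol 4.1.5): AST/ALT above 3×ULN with bilirubin above 2×ULN and ALP below 2×ULN (Hy's law); AST/ALT above 5×ULN for at least 14 days, or above 8×ULN, for subjects with hepatic metastases.
- Post-baseline values are set 0.01 above a threshold.

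**Rules**
- SAP rule: a value above 1×ULN is high, otherwise normal (none of these values is low).
- Multiples rule: bands cut at 1, 2, 3, 5 and 8×ULN. Cuts 2, 3, 5 and 8 come from the documents' thresholds, and 1 is ULN itself. They are illustrative.
- Fold rise = post-baseline value / baseline value.

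| Case | Baseline → post (×ULN) | Fold rise | SAP rule | Multiples rule |
|---|---|---|---|---|
| ALT, no liver metastasis | 2.0 → 3.01 | 3.01/2.0 = 1.5 | high → high | >1–2 → >3–5 |
| ALT, no liver metastasis | 2.0 → 8.01 | 8.01/2.0 = 4.0 | high → high | >1–2 → >8 |
| ALT, liver metastasis | 2.5 → 5.01 | 5.01/2.5 = 2.0 | high → high | >2–3 → >5–8 |
| ALT, liver metastasis | 2.5 → 8.01 | 8.01/2.5 = 3.2 | high → high | >2–3 → >8 |
| Bilirubin | 1.5 → 2.01 | 2.01/1.5 = 1.34 | high → high | >1–2 → >2–3 |
| ALT, normal baseline | 1.0 → 1.01 | 1.01/1.0 = 1.01 | normal → high | ≤1 → >1–2 |
| ALT, normal baseline | 1.0 → 8.01 | 8.01/1.0 = 8.01 | normal → high | ≤1 → >8 |

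Under the SAP rule the five cases with a raised baseline show no shift, and the two normal-baseline cases share one cell. Under the multiples rule all seven move, and the last two are separated.

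**Do other outputs show an isolated ALT rise by ULN multiple?**
- By-visit values and changes (SAP 6.4.3): these cover selected parameters, unnamed, and give no categories.
- By-subject listings (SAP 6.4.3): every value is present, but not summarized.
- Hy's Law listing: it needs bilirubin raised as well.
- TEAE tables by maximum severity (SAP 6.4.2): these are CTCAE-graded, but a laboratory change enters only if the investigator judges it clinically significant. Findings attributed to the underlying disease are left out unless worse than expected (Protocol 8.2.5 and 10.3.1).
- DLT listing (SAP 6.4.2): it covers dose escalation subjects, for related events in Cycle 1. It does not cover backfill subjects, Phase 2 subjects or later cycles.

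None gives a categorical summary of isolated AST or ALT by multiple of ULN.

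**The case against.** The strongest reply is that little depends on this table. It is optional and feeds no dose decision, and the Phase 1 primary endpoints are adverse event incidence, DLTs and the MTD/RP2D. The study is descriptive, and with small cohorts much of the safety review rests on listings. A related ALT rise above 8×ULN in Cycle 1 of escalation, in a subject with hepatic metastases, is a DLT: it is listed, and the subject stops treatment. SAP 1 undertakes to document major modifications, and dropping a supplementary table is arguably not major.

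Most of this stands, and it limits the point. A reader might infer more than the documents support:
- *That liver toxicity is hidden or a primary endpoint compromised.* It is not; the five outputs set out above remain.
- *That the table misses all worsening in anyone out of range at entry.* Shift tables work parameter by parameter. Such a subject can still shift in other parameters, and a two-sided parameter can still show low to high or the reverse. Only same-parameter, same-direction worsening is lost.
- *That 8×ULN is a general DLT limit.* It is written for subjects with hepatic metastases.
- *That the 9.0 g/dL hemoglobin limit puts subjects in the low category.* This is an assumption, since no LLN is given. Coagulation has an out-of-range allowance, but it is scheduled only at screening, so the liver tests are the practical case.

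What the reply does not answer is the mismatch itself. The protocol's commitment is definite, and SAP 8 denies any change without limiting that statement to major ones.

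**Conclusion.** The point holds as a protocol–SAP inconsistency with a limited loss of information. The promised analysis in LLN/ULN multiples is absent from SAP 6.4.3, its substitute is optional and coarser, and SAP 8 is inaccurate on this item. For a parameter already above ULN at entry, any further rise is tabulated as no shift; at the permitted ALT limit with liver metastasis this includes a 3.2-fold rise to 8.01×ULN. For a normal baseline the shift appears without its size.

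The number of subjects affected cannot be stated, because the documents give no distribution of baseline values. The illustration assumes baselines at the entry limits. The conclusion needs only that some subjects enter above ULN, which eligibility permits. The defect should be corrected, but it does not threaten the primary analyses.

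**What to change.** In SAP 6.4.3:
1. Change *may* to *will* for the shift tables.
2. Define the shift as baseline to worst post-baseline value, counting scheduled and unscheduled visits, in prespecified multiples of LLN/ULN.
3. For AST and ALT, use cut-points that include 3×, 5× and 8×ULN. Adding 1× and 2× separates normal from mildly raised values.
4. For total bilirubin, include 1×, 1.5× and 2×ULN and at least one higher category, because a subject with a known genetic cause may enter above 2×ULN and would otherwise have no category to move into. The documents give no figure for the higher cut, so the sponsor must choose it.
5. For ALP, include 2×ULN, the only ALP threshold in the documents.
6. Choose and state LLN multiples for parameters where a fall is the concern; the documents give none.

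Shifts in CTCAE v5.0 grade may be added for other gradable parameters, but they do not replace the multiples that the protocol promised. Any banding leaves change within a band unseen, so the by-visit changes and listings should stay.

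If the sponsor prefers low/normal/high alone, SAP 8 must record this as a change from Protocol 9.2.4.3.

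The cost is SAP wording and one standard table shell. The data are already collected, and no dose, schedule or clinical rule is touched.

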6.4.4 Vital Signs

Vital signs measurements (systolic and diastolic blood pressure, pulse rate, oxygen saturation, body temperature, and weight) will be summarized using descriptive statistics including absolute measurements and changes from baseline by visit.

All vital sign assessments will be presented in a by-subject listing.

6.4.5 Physical Examinations

Results of physical examinations (normal or abnormal) at each time point (including scheduled and unscheduled) will be listed by subject and body system.

6.4.6 ECOG Performance Status

The ECOG performance status at each visit on study will be presented using frequencies and percentages. Both scheduled and unscheduled visits will be tabulated.

ECOG performance status results will be presented in a by-subject listing.

6.4.7 Anti-drug Antibody

The ADA analysis and methods will be described in the Pharmacokinetic and Immunogenicity Analysis Plan.

6.4.8 Concomitant Medications and Procedures

The medications collected will be coded using WHO Drug Dictionary and summarized by ATC and PT. Medications with a stop date before the first dose date will not be included in the summary for concomitant medications. Frequencies and percentages of subjects reporting each PT will be presented by ATC and PT. For each subject, multiple medications with the same PT will be counted once in the summary.

All concomitant medications and medical procedures will be presented in data listings by subject.

6.4.9 Other Safety Assessments

Results from other safety assessments (e.g., pregnancy test) will be presented in by-subject listings if applicable.

6.4.10 Periodic Safety Reporting

The analyses required for DSUR (Development Safety Update Report) and IB (Investigator Brochure) should follow the SAP as applicable. In general, these analyses are subsets of the analyses planned for the CSR.

6.5 Covariates and Subgroups

If the sample sizes permit, subgroup analyses will be performed, at a minimum, for the primary efficacy endpoint (ORR). For the ORR endpoint, forest plots may be provided to assess the consistency of treatment effect by subgroups. The covariates and subgroups of interest include but are not limited to:

- Age, age groups (e.g., <65, ≥65 years)
- Sex at birth
- Number of prior lines of treatment (e.g., 1 versus >1)
- Baseline PD-L1 expression levels (e.g. positive versus negative; >50%)
- Baseline biomarker of disease: carcinoembryonic antigen (CEA) and CA-125 for subjects with NSCLC, CEA and CA19-9 for subject with colorectal or pancreatic cancer, and CA-125 for subjects with ovarian cancer.
- Baseline IHC HYDRA/hypersialylation levels (e.g. combined H-score >50 or >20)

6.6 COVID-19

Protocol deviations resulting from COVID-19 will be recorded and included in the protocol deviation listing.

6.7 Pharmacokinetic Analyses

The PK analysis and methods will be described in the Pharmacokinetic and Immunogenicity Analysis Plan.

6.8 Exploratory Analyses

6.8.1 Exploratory Pharmacodynamic Biomarker Analyses

Exploratory pharmacodynamic biomarker analyses will be performed using the pharmacodynamic evaluable population.

6.8.1.1 Pharmacodynamic Biomarker Definitions

Baseline

For the purposes of the pharmacodynamic biomarker analyses, baseline will be defined as indicated for each parameter:

- Chemokine Panel, Pro-inflammatory Panel, and C3a: last non-missing measurement prior to the first administration of E-602 treatment.
- Immunophenotyping parameters: Average of non-missing measurements prior to the first administration of E-602 treatment or the only available measurement prior to the first administration of E-602 should only one measurement be available.
- IHC: last non-missing measurement prior to the first administration of E-602 treatment.

Fold-change from Baseline

Fold-change from baseline is the ratio of the post-baseline value over the baseline value.

Fold-change from Baseline = Post-baseline Value/Baseline Value.

*Note: "value" in MFI of PNA = MFI (timepoint) - MFI (FMO)

Data Handling and Exclusions

The following quality metrics will be used to exclude entire visit/timepoint results from the analysis. Any visit/timepoint meeting the exclusion criteria will be noted in the listing of the corresponding Biomarker Panel.

Biomarker Panel	Exclusion Criteria
Immunophenotyping (FACS)	<65% live cells by Cellometer count OR Received for PBMC processing >72 hours after collection
Tissue IHC	H&E Adequacy = "N"

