- 20. Fresh tumor biopsy is required for all subjects in Phase 1 combination at screening and on Cycle 2 Day 1 post-dose (+4 days). Fresh tumor biopsy is required for all subjects in Phase 2 at screening and post-dose on Cycle 2 Day 1 or Day 8. The biopsy should be performed on Day 2 or 3 if performed post Cycle 2 Day 1 E-602 administration or Day 9 or 10 if performed post Cycle 2 Day 8 E-602 administration. An archive tissue sample is required for all subjects. See Section 8.5.3 for further information.
- 21. Dosing visits should not be skipped due to dose delays.
- 22. Unscheduled cytokine panel samples should be collected in the event of an infusion related reaction.

2. Introduction

E-602, also known as Bi-Sialidase,

E-602 is being developed as an immune therapy to treat

advanced cancers.

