- Changes in the glycoproteomic profile

These samples may also be used for other biomarker research to further elucidate E-602 mechanism of action, identify potential resistance mechanisms, understand variability in response and/or adverse events, identify other biomarkers of response, and to better understand the disease understudy. Analyses may include, but are not limited to protein, metabolite and antibody profiling methodologies.

Additional exploratory biomarkers related to tumor and immune biology may be analyzed, using methods such as gene expression profiling, mutational, protein and tissue image analysis.

^bThe 0.5 h sample collection is \pm 5 mins from the end of E-602 infusion. In instances when the infusion time is >30 minutes, the \pm 5 mins window still applies to the end of the infusion.

^{&#}x27;In the event the E-602 infusion exceeds 2 hours, the 2 h timepoint will be permitted as a missed assessment.

^dThe 6 h sample is only required for Phase 1 E-602 monotherapy cohorts.

^eCycle 1 Day 3 and Cycle 2 Day 10 sample collection is not required for Phase 2.

Details of sample collection, storage, and shipping instructions will be provided in the Laboratory Manual.

Table 4 Phase 1 E-602 monotherapy biomarker sample collection time points for pharmacodynamic, genetic and immunogenicity analyses

Cycle	Day	Time ^a	Cytokine Panels and C3a	FACS (desialylation and activation)	RNASeq (blood)	Circulating Tumor DNA	Tumor Biopsy	ADA	Glycoproteomic Profile
Screening							X		
1	1	predose	X ^b	Xb	X ^b	Xb		X	X
	2	$24\ h\pm 2\ h$	X	X	X				X
	3	$48\ h\pm 4\ h$	X	X	X				X
	8	predose	X	X	X				X
	9	$24\ h\pm 2\ h$	X	X	X				X
	10	$48\ h\pm 4\ h$	X	X	X				X
	15	predose	X	X	X				X
2	1 (Day 22)	predose					X	X	
≥ 3	1	predose				Xc		X	
EOT	NA	NA						X	
Follow- up 30 day	NA	NA						X	

^aAll time points except predose are after the start of infusion.

Table 5 Phase 1 combination and Phase 2 biomarker sample collection time points for pharmacodynamic, genetic and immunogenicity analyses

Cycle	Day	Time ^a	Cytokine Panels and C3a	(desialylation	SNPs	Circulating Tumor DNA	Tumor Biopsy	ADA	Glycoproteomic Profile
Screening							X^d		
1	1	predose	X ^b	X^b	X	Xb		X	X
	2	24 h ± 2 h	X	X					X
	8	predose	X	X					X
	9	24 h ± 2 h	X	X					X
	15	predose	X	X			_		X

^bTwo predose samples should be collected at least 1 hour apart and up to 72 hours prior to Cycle 1 Day 1.

^cCirculating tumor DNA samples will be collected with radiological assessments.

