8.5.2. Genetics

Blood samples in the Phase 1 E-602 monotherapy portion of the study will be collected to analyze circulating tumor DNA for target gene expression and immune cell gene expression profiling (RNAseq) at timepoints specified in the SoA and in Table 4.

Table 5 summarizes the blood sample collection in Phase 1 combination and Phase 2 including collection of samples for circulating tumor DNA assessment and a whole blood single nucleotide polymorphism (SNP) sample for DNA sequencing.

The SNP sample will be used to assess genetic variation or single nucleotide polymorphisms in select genes, including and not limited to genes involved in the metabolism and catabolism of sialoglycans and glycoproteins (i.e., glycogenes) or other genes that may predispose subjects to E-602 benefit or adverse events. Additional uses of the DNA sequencing data from the whole blood SNP sample may include correlations with clinically-relevant biomarkers identified by other methodologies described in this section to identify genotypic associations, as well as for comparison to tumor mutation data to identify genetic variants specific to the tumor.

These blood samples may also be used for other pharmacogenomic/biomarker research to further elucidate E-602 mechanism of action, identify potential resistance mechanisms, understand variability in response and/or adverse events, identify other biomarkers of response, and to better understand the disease under study.

^bTwo predose samples (prior to start of any study treatment administration) should be collected at least 1 hour apart and up to 72 hours prior to Cycle 1 Day 1.

^cCirculating tumor DNA samples will be collected with radiological assessments and at EOT visit.

^dFresh tumor biopsy is required for all subjects in Phase 1 combination at screening and on Cycle 2 Day 1 post-dose (+4 days). Fresh tumor biopsy is required for all subjects in Phase 2 at screening and post dose on Cycle 2 Day 1 or Day 8. The biopsy should be performed on Day 2 or 3 if performed post Cycle 2 Day 1 E-602 administration or Day 9 or 10 if performed post Cycle 2 Day 8 E-602 administration. An archive tissue sample is required for all subjects.

Tissue samples (Section 8.5.3) may also be analyzed for immune cell gene expression profiling (RNAseq) and tumor mutational burden.

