6.8.1.2 Pharmacodynamic Biomarker Analysis

Immunophenotyping (FACS), Chemokine Panel, Pro-inflammatory Panel and C3a biomarkers will be summarized using descriptive statistics for select parameters including absolute measurements and fold change from baseline by visit. Tissue IHC biomarkers will be summarized using descriptive statistics for select parameters including absolute measurements and change from baseline.

Sensitivity pharmacodynamic biomarker analyses may also be performed. For Tissue IHC biomarkers, data may be summarized for the patients for which there are matched pre- and on-treatment and the on-treatment biopsy was collected within 48 hours after the last dose of E-602. All biomarker results will be presented in a by-subject listing.

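### The cytokine, chemokine and C3a baseline uses one of two predose samples and is anchored on E-602, so in combination cohorts a cytokine baseline can fall after cemiplimab

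*SAP*

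**What the plan says.** SAP 6.8.1.1 gives a separate baseline rule for each assay group.

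- Cytokine-type panels and complement: "Chemokine Panel, Pro-inflammatory Panel, and C3a: last non-missing measurement prior to the first administration of E-602 treatment".
- FACS: "Immunophenotyping parameters: Average of non-missing measurements prior to the first administration of E-602 treatment", or the single value if only one exists.

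The blood sampling behind the two rules is the same. In Protocol Table 4 (Phase 1 monotherapy), footnote b is attached to the Cycle 1 Day 1 predose entries for both cytokine/C3a and FACS. It asks for two samples: "predose samples should be collected at least 1 hour apart and up to 72 hours prior to Cycle 1 Day 1". Table 5 (Phase 1 combination and Phase 2) carries the same requirement: "should be collected at least 1 hour apart and up to 72 hours prior to Cycle 1 Day 1". It adds that both samples precede any study treatment.

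The derived variable is a raw ratio: "Fold-change from Baseline = Post-baseline Value/Baseline Value". Under SAP 6.8.1.2 these biomarkers "will be summarized using descriptive statistics for select parameters including absolute measurements and fold change from baseline by visit".

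Protocol 1.3.2, footnote 22, adds: "Unscheduled cytokine panel samples should be collected in the event of an infusion related reaction". Protocol 10.5 repeats this for infusion reactions generally.

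**The concern.** There are two separate weaknesses in one line of the SAP.

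First, every subject is asked for two predose cytokine/C3a samples, but the fold change uses only one. For FACS the same pair is averaged. The SAP gives no reason for the difference.

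Second, the cytokine rule looks back from the first E-602 dose. In combination cohorts that is not the first study drug. A value obtained after cemiplimab but before E-602 would satisfy the definition. If it was drawn because of a reaction, it may be raised. It would then be the denominator of every later fold change for that subject and would shrink any later rise.

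What is at stake is the precision and meaning of an exploratory endpoint, change in cytokine levels. The protocol rationale says E-602 does not cause cytokine activation, and Protocol 2.3 reports infusion reactions in 12 of 26 treated subjects at 10 mg/kg or above. These fold changes are therefore of interest even though no formal conclusion depends on them.

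**Working it through.** **Anchor: the passages side by side**

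1. Order of drugs: cemiplimab first, then E-602 no sooner than 30 minutes after that infusion ends (Protocol 4.1.1 and 6.5).
2. Reactions to either drug are foreseen and are watched for until one hour after an infusion ends (Protocol 6.6).
3. A reaction calls for an unscheduled cytokine panel sample (Protocol 1.3.2 footnote 22 and 10.5).
4. The cytokine baseline is the latest value before E-602, and nothing limits it to scheduled samples (SAP 6.8.1.1).
5. Hence a cytokine sample drawn between the start of cemiplimab and the start of E-602 replaces both scheduled predose values.

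Three other definitions point the other way. The general baseline in SAP 4.4 precedes the first study treatment. SAP 3 dates the first dose in combination subjects from cemiplimab. Protocol Table 5, footnote a, places predose sampling ahead of any study drug.

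Suppose the reaction-triggered value is c times the true predose level, with c > 1. Under the current rule each later fold change is multiplied by 1/c. If the values were averaged but the E-602 anchor kept, the baseline would be (1 + 1 + c)/3 and the multiplier 3/(2 + c), which is still below 1. Averaging alone does not cure the anchor; it has to move as well.

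Phase 1 escalation cohorts have 3 to 6 subjects, so one affected subject carries between 1/3 and 1/6 of a by-visit mean.

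**Averaging: what it could gain**

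The plan states no SD, CV, correlation or precision for these biomarkers, so there is no figure to reproduce. All inputs below are assumptions.

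Let the log-scale error variance be s² at each measurement, r the correlation between the errors of the two predose samples, and h·s² the true between-subject variance of log fold change.

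- Last value: s²(1 + 1 + h)
- Mean of two: s²(1 + (1 + r)/2 + h)
- Relative reduction: [(1 − r)/2] / (2 + h), which is (1 − r)/4 when h = 0

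| r | h = 0 | h = 1 |
|---|---|---|
| 0 | 1 − 1.5/2 = 25% | 1 − 2.5/3 = 16.7% |
| 0.5 | 1 − 1.75/2 = 12.5% | 1 − 2.75/3 = 8.3% |
| 0.8 | 1 − 1.9/2 = 5% | 1 − 2.9/3 = 3.3% |

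The SAP's fold change is a raw ratio. It was simulated with lognormal errors, h = 0 and an arithmetic-mean baseline (4,000,000 draws per setting).

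| r | Reduction at CV 10% | Reduction at CV 50% |
|---|---|---|
| 0 | 25.9% | 42.0% |
| 0.5 | 13.1% | 23.6% |
| 0.8 | 5.2% | 10.2% |

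**When averaging does not help**

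Let the post-dose value correlate a with the later predose sample and b with the earlier one, and let the predose pair correlate d, with equal variances. In units of the common variance:

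- Last value: 2 − 2a
- Mean of two: 1 + (1 + d)/2 − (a + b)

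Averaging lowers the variance only if a − b < (1 − d)/2. With a = 0.7, b = 0.5 and d = 0.8, the two variances are 0.6 and 0.7, so averaging raises the variance by 16.7%. With a = 0.6 and the same b and d, both are 0.8 and nothing is gained.

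**The case against.** The last-value rule is the SAP's ordinary convention. SAP 4.4 uses it by default and IHC follows it, so FACS is the exception. Both rules are prespecified and reproducible, and choosing between them is partly preference. All biomarker results are listed by subject, absolute values are summarised beside the fold changes, and sensitivity biomarker analyses are permitted, so a careful reader could see both predose values and any reaction-triggered one. The contamination route is narrow: it needs a combination subject, a cemiplimab reaction, a sample drawn in the gap, and E-602 given afterwards.

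Most of this stands and keeps the point small. It does not repair the rule. The fold changes are still computed from the defined baseline, the sensitivity analyses are optional and none is specified for this, and the cytokine rule does not follow SAP 4.4 on the anchor.

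A reader might also infer more than the documents support:

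- **A fixed loss of up to 25%.** That figure needs log scale, equal and independent errors, and no true between-subject variation. Samples that may be only one hour apart could well be correlated. Nor is it a ceiling, since the raw ratio can exceed it.
- **A cost in subjects.** Inverting 25% gives 1/0.75 = 1.33, or 33% more subjects, but no test or sample size depends on this endpoint.
- **A hidden safety signal.** SAP 6.4 bases safety on adverse events, laboratory tests, vital signs, examinations and ECOG status, and the DLT criteria contain no cytokine measure.
- **FACS as a full model.** Its rule supplies the averaging only. It names no log scale and has the same E-602 anchor.
- **Contaminated C3a.** The unscheduled-sample text names cytokine panels, so contamination of C3a is not established.

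**Conclusion.** The point holds as a minor but real defect of definition. Two predose samples are required, one is left out of the fold change without explanation, and the E-602 anchor lets a post-cemiplimab cytokine value serve as baseline. The anchor problem rests on the text alone. Its frequency cannot be estimated from the documents and is probably low.

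The precision gain is conditional: 25%, 12.5% or 5% lower log-scale variance at r = 0, 0.5 or 0.8 under equal errors and no true between-subject variation. The log-scale gain is smaller if subjects truly differ in fold change, and it can be nil or negative if the later sample tracks the post-dose value better. Because the analysis is exploratory and descriptive, type I error, power, sample size and every decision rule are unaffected.

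**What to change.** Amend SAP 6.8.1.1 as follows.

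- Chemokine, pro-inflammatory and C3a panels: baseline is the average of all available values from samples taken before the first dose of any study treatment, whether cemiplimab or E-602. Use the geometric mean if fold change is analysed on the log scale. If only one value exists, use it.
- Immunophenotyping: keep the average and move its anchor to the same point.
- Sensitivity analysis: repeat the cytokine, chemokine and C3a fold changes with the last value before any study treatment as baseline.

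If the sponsor prefers the last value as the main rule, state why and still move the anchor. The cost is a few lines of SAP text and one extra derivation. The protocol already requires both samples, so no further collection is needed.
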